#### 7.2.2 Identification of potential participants and screening at secondary care sites

Potential participants will also be identified at the secondary care centres, i.e. hospital standard vulval clinics or community hubs (such as gynaecology or dermatology centres), where staff are experienced in the management of vulval skin disorders. The information about the trial will be displayed in the relevant clinical areas at hospitals or community hubs.

At the secondary care centres, patients will be identified and approached by their clinical care team, where possible in advance of their next appointment, however they may also be identified while attending routine clinic appointments and will be offered the opportunity to meet the site team investigator or a research nurse for further information.

Following the identification of patients by the clinical care team, an invitation letter (which will include appropriate instructions how to express interest in the trial), along with the PIS, will be provided to the patient. Once the patient has expressed interest, and agreed to be contacted, a site team member will get in touch (usually by phone or face-to-face at the patient's clinic appointment) to perform basic eligibility checks (e.g. symptom free, willing to travel) and willingness to participate. Participants' contact details of those who do not consent for us to retain them, will be deleted at the end of the trial.

### 7.2.3 Self referrals

Potential patients, who have been diagnosed with LS and found the trial details via the routes described in 7.1 above, may be able to self-refer. They will be able to get in touch with the study team directly or log their interest to be contacted by a central research team or a team at a secondary care site. Patients who self-refer will be pre-screened and provided with a PIS, if appropriate, and a suitable secondary care site will arrange a screening visit (eligibility check).

#### Screening for eligibility criteria

Once patients (identified through either PICs, self-referral or secondary care centres) confirm their expression of interest, they will be invited by site team to their first, screening/baseline visit. At this visit, the trial will be discussed in more detail and, if agreed, informed consent will be taken.

Following informed consent (section 7.9), eligibility will be confirmed by a site investigator, a medically qualified doctor, and baseline data will be collected. A physical investigation will be conducted to confirm diagnosis. Patients will be asked to confirm that they are symptom-free. Other eligibility criteria will be confirmed from medical notes or discussion. If the patient meets all eligibility criteria, they will be randomised to the trial treatment at which point the participant trial unique number will be allocated.

Those who do not meet the trial eligibility criteria, or do not wish to participate in the trial, not be randomised and will be excluded from the trial.

### 7.3 Participant identification and screening logs

The site team at the trial centres will maintain a list of potentially eligible participants who were identified through self-referrals, PICs or secondary care centres and were approached to discuss the trial. The sites will upload anonymised data (totals) from the logs on monthly basis on the trial database.

The trial central coordinating team, at the NCTU, may request the identification and screening logs from the sites, for monitoring purposes. The sites will redact any personal identifiable information from the logs prior to sending to the NCTU.

### 7.4 Eligibility criteria

#### 7.4.1 Inclusion criteria

1. Clinical or biopsy confirmed diagnosis of vulval LS
2. Currently controlled disease (asymptomatic with minimal clinical evidence of active disease) at baseline
3. Age  $\geq 5$  years
4. Able to give consent/child assent plus parental consent

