#### **1.4 Rationale of the trial**

The trial will address two priorities from the 2018 Lichen Sclerosus Priority Setting Partnership [24]: a) What is the best way to prevent and manage anatomical changes caused by LS? b) Is it necessary to continue treatment for patients with LS who do not have any symptoms and/or signs of disease activity?

There are no robust long term RCTs to compare proactive against reactive TCS therapy for LS. An observational study [25] suggests symptoms and scarring are reduced by proactive therapy. Another small study (n=27) reports 60% of patients using only emollients will have a relapse compared with none using proactive TCS over one year [26].

Alternative topical treatment options are either unsuitable or ineffective [21, 23]. Topical calcineurin inhibitors pose theoretical increased risk of cancer due to their immunosuppressant effects on T cells. Topical retinoids are irritant to vulval skin, furthermore retinoids are teratogenic and therefore unsuitable for large proportion of LS sufferers. Topical testosterone has not been found to be effective. At present, there are no other known topical agents on the horizon for first line treatment of LS. As a result, TCS, which are inexpensive, effective and well understood, remain the mainstay of LS treatment. Optimising their usage and standardising advice given to patients is important.

The PEARLS Trial will compare reactive and proactive TCS maintenance strategies in a superiority trial of proactive over reactive treatment. The trial recruitment will be from primary and secondary care, including both women and girls  $\geq 5$  years of age with vulval LS. Due to differences in management and outcomes between male and female patients and reduced prevalence of LS in males, only female patients will be included. Paediatric patients are included, due to even greater paucity of evidence for this subset. There is a clear peak of incidence in girls aged four to six years old, which represents 7–15% of all vulvar lichen sclerosus cases [27]. The only published randomised control trial with paediatric patients enrolled only a handful of children and reported their data together with adult participants, making it impossible to draw any conclusions about the prepubertal patients [28]. Follow-up will be for 2 years to assess for scarring, with optional consent obtained for longer term outcomes and economic modelling (separate funding to be sought if appropriate).

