## 2 DETAILS OF INVESTIGATIONAL MEDICINAL PRODUCT(S) (IMP)

### 2.1 Description

Participants will be randomised to one of two treatment strategies:

**Intervention group:** Potent or superpotent topical corticosteroid (TCS) to be applied on two non-consecutive days per week even in the absence of symptoms (proactive).

**Comparator group:** Potent or superpotent topical corticosteroid (TCS) to be applied as required to treat a LS flare (reactive).

More details on the treatment strategies are described in Table 6. Intervention vs comparator group. Choice of TCS will be according to the patient's usual care and the trial will test TCS as a class defined by their Anatomical Therapeutic Chemical (ATC) classification numbers D07AC and D07AD (for potent and superpotent respectively). As this is a pragmatic trial, we will test the strategy of proactive vs reactive treatment using the potency of topical corticosteroid recommended by the treating clinician (potent or superpotent). There are several generic names available for these prescribed TCSs and all available brands and forms can be prescribed. The examples of the most commonly prescribed brands/products of the TCS class are listed below (for details see Table 1):

- Dermovate ointment - superpotent TCS
- Elocon® 0.1% w/w ointment - potent TCS

Table 1. Potent and superpotent TCSs description

Name of exemplar product	International Non-Proprietary Name (INN)	Potency	Chemical name or CAS number	Formulation	Excipients	ATC code	Chemical and pharmacological properties	Manufacturer and MA (Marketing Authorisation) number
Dermovate ointment	Clobetasol 17-propionate 0.05375% w/w	Superpotent	25122-46-7	Ointment	Propylene glycol, Sorbitan sesquioleate, White soft paraffin.	D07AD01	Pharmacotherapeutic group: Corticosteroids, very potent, dermatological preparations (group IV). Topical anti-inflammatory activity. The major effect on skin is a non-specific anti-inflammatory response, partially due to vasoconstriction and decrease in collagen synthesis.	Manufacturer: GlaxoSmithKline UK  MA number: PL 10949/0028

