## 5 RANDOMISATION AND BLINDING

Upon entry to the trial, participants will be individually allocated in a 1:1 ratio to either proactive or reactive use of TCS. The strategies of treatment will be assigned randomly using a minimisation algorithm with a random element, balancing across groups on:

- Recruitment by site
- Age at randomisation (prepubertal – 5 to <12 years, adolescent - 12 to <16 years, adult - 16 to <45 years, perimenopausal 45 years & above)
- Time since last flare ( $\leq 6$  months,  $> 6$  months)
- Strength of study TCS (potent or superpotent)

The trial arm allocation will be concealed using a web-based algorithm and will be held on a secure server at the Nottingham Clinical Trial Unit (NCTU). The randomisation will be accessed via a secure website developed and maintained by NCTU. Unique usernames and passwords will be provided to those who are delegated the role of randomising participants using the web-based system. Randomisation can be performed by suitably trained site research staff assigned this task on the *Delegation of Responsibilities Log*, following confirmation of each individual participant's eligibility by a clinician.

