#### 7.4.2 Exclusion criteria

1. Previous vulval intraepithelial neoplasia (VIN) or vulval squamous cell carcinoma (SCC)
2. Contraindications to topical steroids
3. Concomitant use of other topical anti-inflammatory vulval treatments
4. Using systemic immunosuppressants (for any indication)
5. Using systemic treatment for LS
6. Patients with surgical alteration of vulval skin as part of gender reaffirming surgery, or patients not born with a vulva
7. Pregnant and breastfeeding women

The trial inclusion criteria are designed to mimic usual practice. LS is a clinical diagnosis and biopsy is only performed if there is a poor response to first-line treatment, diagnostic doubt or concern of pre-malignancy/malignancy. Those patients who are asymptomatic and with minimal evidence of active disease at baseline are considered to be well-controlled. Girls aged 5 or older will be included as there is paucity of evidence for LS management in paediatric patients.

By definition, anyone with previous vulval intraepithelial neoplasia, or vulval cancer, have complicated LS, are not eligible for the trial. If there is sensitivity to topical corticosteroids entering the trial might worsen this. Finally, other anti-inflammatory agents, topical or systemic, would act as a confounder, and patients on these treatments are more likely to have complicated disease.

In accordance with the Clinical Trial Facilitation Group "recommendations related to contraception and pregnancy testing in trials", given that the trial IMPs are all licensed products, participants of child-bearing potential can be included in the trial providing an acceptable effective method of contraception is used until treatment discontinuation. Acceptable contraceptive methods include: established use of oral, injected or implanted hormonal methods; placement of an intrauterine device (IUD) or intrauterine system (IUS); condom or occlusive cap (diaphragm or cervical/vault caps) with spermicide; true abstinence (when this is in line with the preferred and usual lifestyle of the participant); or vasectomised partner. Participants will be advised of the importance of these requirements before entry into the trial. The trial IMPs are licensed products which are routinely prescribed to pregnant women therefore a pregnancy test will not be required before entry to the trial, but the participant should contact their GP and seek further direction if pregnancy should subsequently be confirmed.

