### Baseline

#### Visit 1

(at baseline)

- Informed consent
- Eligibility check and confirmation
- Contact details
- Collection of baseline data:
  - Concomitant medication (relevant to condition) and relevant medical history
  - Demographic information
  - Clinician global severity assessment
  - Scarring assessment (VASS, clinical examination)
  - Vulval development and scarring (in adolescents and children)
  - Condition specific QoL (VQLI or CDQLI)
  - Health related QoL assessed by EQ-5D-5L in adolescents/adults and CHU-9D in children
  - Bespoke resource use questionnaire and healthcare questionnaire
- Clinical photographs, or clinical diagram if consent for photographs not taken
- Randomisation

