### 10.5 Planned subgroup analyses

Subgroup analyses for the primary outcomes will be performed according to age at randomisation (children (<16 years) or adults ( $\geq 16$ )), time since last flare ( $\leq 6$  months,  $> 6$  months), and strength of study TCS (potent or superpotent) by including appropriate interaction terms in the regression models. The trial is not powered to detect any interactions hence the subgroup analyses will be treated as exploratory.

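### The primary model uses flare history only as a 6-month cut, and pre-entry steroid regimen and prior flare count are not named baseline items: an avoidable loss of precision and description, not a flaw in validity

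*Protocol*

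**What the plan says.** **Entry.** Inclusion requires "Currently controlled disease (asymptomatic with minimal clinical evidence of active disease) at baseline" (7.4.1), with no minimum duration of control and no condition on how it was achieved. The only exclusion on topical treatment is "Concomitant use of other topical anti-inflammatory vulval treatments" (7.4.2), so existing topical corticosteroid (TCS) maintenance is allowed. Section 2.1 adds: "Choice of TCS will be according to the patient's usual care".

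**Timing.** There is no run-in. Under Screening for eligibility criteria, "If the patient meets all eligibility criteria, they will be randomised to the trial treatment", and 8.1 places consent, eligibility check and randomisation at Visit 1.

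**Allocation and model.** Section 5 minimises on site, age band, "Time since last flare" (6 months or less, or more) and TCS potency. Section 10.2 specifies a negative binomial model giving one rate ratio, adjusted for those factors.

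**Subgroups.** Section 10.5 states: "Subgroup analyses for the primary outcomes will be performed according to age at randomisation", and goes on to time since last flare and potency. Section 10.2 leaves further subgroups to the SAP.

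**Baseline data.** Visit 1 lists "Concomitant medication (relevant to condition) and relevant medical history". Neither the regimen in use before entry nor a count of earlier flares is named.

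**Rationale.** Section 1.4 cites the question "Is it necessary to continue treatment for patients with LS who do not have any symptoms and/or signs of disease activity".

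**The concern.** A patient may be controlled at Visit 1 because she uses TCS regularly, because she has just completed daily induction, or because she is in remission without treatment. For the first, allocation to reactive use is a withdrawal and allocation to proactive use is roughly no change. For the last, proactive use is new and reactive use is roughly no change. Potency does not record this. Nor does time since last flare: a patient flare-free on maintenance and one flare-free off treatment share a level.

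Two things are at stake. If the regimen is not captured before randomisation, readers cannot see what mix of patients the rate ratio averages over. And a person's earlier flare count probably predicts her later count better than a two-level time cut, so leaving it out gives up precision that costs little to obtain.

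**Working it through.** **Inputs from Protocol 10.1.** Control rate 4 per year, intervention rate 3, dispersion k = 0.34, 90% power, two-sided 0.05, 1:1 allocation, 320 for analysis, 400 randomised.

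**Step 1. The planned size reproduces.**
- n per arm = (1.960 + 1.282)² × (1/4 + 1/3 + 2 × 0.34) / (ln 0.75)² = 160.4, or 322 in total.
- With the null variance evaluated at the mean rate of 3.5, n = 159.5 per arm, or 320 in total.
- Power at 160 per arm is 89.9%.
- 320 / 0.80 = 400.

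None of this relies on the prior flare count, so the sample size is not in question.

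**Step 2. How the 6-month cut splits patients.** If entrants' rates follow the survey's distribution, the expected count in 6 months is 2, and

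P(no flare in 6 months) = (1 + 0.34 × 2)^(−1/0.34) = 1.68^(−2.94) = 0.217.

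About 78% would be in the level of 6 months or less. With stable personal rates, mean rates in the two levels are about 4.4 and 2.4 per year, and adjusting for the cut lowers residual dispersion from 0.34 to 0.28. The cut therefore carries some of the information.

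**Step 3. What the count would add.** Gamma-Poisson simulation with n = 320, mean 4, k = 0.34 and rate ratio 0.75. The negative binomial model with the 6-month split is compared with the same model plus the prior 12-month count. The year-to-year correlation of a person's underlying rate is assumed; the Protocol gives no figure.

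| Rate correlation | SE of log rate ratio, split only | SE, plus prior count | Variance reduction, 1 − (SE ratio)² |
|---|---|---|---|
| 1 | 0.0847 | 0.0746 | 22–23% |
| 0.7 | 0.0867 | 0.0824 | 10% |
| 0.5 | 0.0876 | 0.0857 | 4% |

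For example, 1 − (0.0824/0.0867)² = 0.097. A separate approximation, based on residual dispersion and imposing no functional form on the count, gives larger gains. The total N for 90% power is 292 with the split and 210 with the count under stable rates, 304 and 256 at correlation 0.75, and 314 and 292 at 0.5. The direction and the dependence on stability agree; the simulated figures are the more cautious.

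**Step 4. What a prior-regimen subgroup could show.** All values here are assumed: half of entrants on maintenance, and equal control rates. For rate ratios of 0.60 (on maintenance) and 0.90 (not), interaction power at 320 is 62%. For 0.65 and 0.85 it is 32%. Such a subgroup would be descriptive.

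**The case against.** **The mixed population is intended.** Section 7.4.2 says that the inclusion criteria follow usual practice, and 3.2 compares strategies in people with vulval LS. An average strategy effect in controlled patients is a proper target. This stands, and it is why entry criteria and the absence of a run-in are not criticised.

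**Flare history is already used.** Time since last flare is a minimisation factor, a covariate and a subgroup. This also stands; the point is only that the cut is coarse.

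**The rest can go in the SAP, and the data may exist.** Section 10.2 reserves further subgroups for the SAP, and 8.2 documents relevant medication on entry. The Visit 1 list is not exhaustive: it omits time since last flare and TCS strength, which randomisation needs. So its silence does not prove that regimen goes unrecorded. This stands in part. But the covariate set is fixed in 10.2, a medication entry need not show whether use was regular or as required, and a SAP agreed shortly before database lock cannot recover items not asked before randomisation.

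**A stronger reading.** A reader might infer that the pooled ratio describes no one and that the trial cannot answer the question in 1.4. With assumed ratios of 0.60 on maintenance and 0.90 otherwise, the pooled value is 0.825, 0.75 or 0.675 when 25%, 50% or 75% enter on maintenance (for example 0.5 × 0.60 + 0.5 × 0.90 = 0.75), with power at 320 of 59%, 90% or 99%. The Protocol gives neither the share on maintenance nor any regimen-specific effect, so these figures show what could happen and are not evidence that it does. The primary objective also does not promise separate answers for those stopping and those starting maintenance.

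**Conclusion.** The point holds as a modest improvement to baseline capture and covariate adjustment. The variance of the log rate ratio would fall by about 23%, 10% or 4% at rate correlations of 1, 0.7 or 0.5, before any allowance for recall error. The 78% figure assumes that entrants selected as controlled have the survey's flare distribution, which the Protocol does not establish.

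A reader might go further and call the prior count a strong predictor that has been wrongly omitted, or treat the comparison as biased. Neither is supported. The strength depends on a year-to-year stability that the documents do not report, and at correlation 0.5 the gain is small. Randomisation protects the comparison whatever the regimen mix, and 320 reproduces without the extra covariate.

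**What to change.** 1. **8.1, Visit 1, before randomisation:** add two named items. These are the TCS regimen over the previous 6 months (regular maintenance, as required, induction just completed, none) and the number of flares in the previous 12 months.
2. **10.2:** add log(prior flares + 0.5) and prior regimen to the primary model as prespecified covariates alongside the minimisation factors, and report the regimen mix by arm with the other baseline descriptives.
3. **10.5:** list prior regimen (maintenance or not) as one more exploratory subgroup, stating that its power is low.

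Leave eligibility, minimisation and the absence of a run-in unchanged.

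The cost is two baseline questions, one covariate line and one subgroup line. The downside is recall error in the prior count. Because it is recorded before allocation, that error reduces the gain but does not bias the comparison. If recruitment has already begun, check first whether the existing medication and history entries allow the regimen to be coded from information recorded before randomisation.

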#### 7.4.2 Exclusion criteria

1. Previous vulval intraepithelial neoplasia (VIN) or vulval squamous cell carcinoma (SCC)
2. Contraindications to topical steroids
3. Concomitant use of other topical anti-inflammatory vulval treatments
4. Using systemic immunosuppressants (for any indication)
5. Using systemic treatment for LS
6. Patients with surgical alteration of vulval skin as part of gender reaffirming surgery, or patients not born with a vulva
7. Pregnant and breastfeeding women

The trial inclusion criteria are designed to mimic usual practice. LS is a clinical diagnosis and biopsy is only performed if there is a poor response to first-line treatment, diagnostic doubt or concern of pre-malignancy/malignancy. Those patients who are asymptomatic and with minimal evidence of active disease at baseline are considered to be well-controlled. Girls aged 5 or older will be included as there is paucity of evidence for LS management in paediatric patients.

By definition, anyone with previous vulval intraepithelial neoplasia, or vulval cancer, have complicated LS, are not eligible for the trial. If there is sensitivity to topical corticosteroids entering the trial might worsen this. Finally, other anti-inflammatory agents, topical or systemic, would act as a confounder, and patients on these treatments are more likely to have complicated disease.

In accordance with the Clinical Trial Facilitation Group "recommendations related to contraception and pregnancy testing in trials", given that the trial IMPs are all licensed products, participants of child-bearing potential can be included in the trial providing an acceptable effective method of contraception is used until treatment discontinuation. Acceptable contraceptive methods include: established use of oral, injected or implanted hormonal methods; placement of an intrauterine device (IUD) or intrauterine system (IUS); condom or occlusive cap (diaphragm or cervical/vault caps) with spermicide; true abstinence (when this is in line with the preferred and usual lifestyle of the participant); or vasectomised partner. Participants will be advised of the importance of these requirements before entry into the trial. The trial IMPs are licensed products which are routinely prescribed to pregnant women therefore a pregnancy test will not be required before entry to the trial, but the participant should contact their GP and seek further direction if pregnancy should subsequently be confirmed.

Disease progression will be assessed, monitored and analysed based on characteristic anatomical features of the vulva. For this reason, patients who were born with a vulva (which has not been altered as part of gender affirming surgery) can be considered to be included in the trial.

